9.4.4 SAFETY ANALYSES

Data will be reported on specific safety outcomes that may be related to caffeine. Despite the high safety profile associated with caffeine, certain risks have been associated with administration (see **Section 2.3, Risk/Benefit Assessment**). The following adverse events that may occur with caffeine will be reported:

Outcome	Measure
New cardiac arrhythmia (e.g., supraventricular tachycardia, ventricular tachycardia) incidence	Incidence (%)
SBP (mm Hg)*	n (SD)
DBP (mm Hg)*	n (SD)

The CAffeine, Postoperative Delirium, And CHange IN Outcomes after Surgery-2 (CAPACHINOS-2) Study Protocol <2.0>

Version <2.0>
<14 December 2022>

HR (BPM)*	n (SD)
Restraint use	Incidence (%)
Injury to self or others	Incidence (%)
Postoperative Nausea and Vomiting**	Score (n)
Dehydration†	Incidence (%)
Allergic Reaction‡	Incidence (%)

*Vitals will be presented as descriptive statistics – no cutoff thresholds will be assigned. **Via Postoperative Nausea and Vomiting Intensity Scale. †Dehydration will be recorded if this term is described in the medical record by clinical teams caring for the patient. ‡The nature of any suspected allergic reaction will be reported in full detail.

The study drug will be discontinued in the event of new-onset cardiac arrhythmia, suspected allergic reaction, or any other concern raised by either the clinical or research team. Adverse events will otherwise be coded as described in **Section 8.3, Adverse Events and Serious Adverse Events**.

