2.3 RISK/BENEFIT ASSESSMENT

2.3.1 KNOWN POTENTIAL RISKS

Contraindications, drug interactions, and adverse reactions are described in the caffeine citrate package insert (<https://dailymed.nlm.nih.gov/dailymed/drugInfo.cfm?setid=38b39044-737a-4247-a6c4-c86f5e92490e&audience=consumer>). Primary risks described relate to the pediatric (neonatal) population, which will not be included in this trial.

In the acute setting, caffeine has been associated with various side effects. As mentioned previously, Steinbrook et al. demonstrated that perioperative caffeine may increase the risk of nausea, though participants randomized to caffeine experienced neither an increased risk of vomiting nor increased rescue antiemetic use.³² Lagier et al. also demonstrated that postoperative caffeine may increase nausea and vomiting risk; however, the dose and frequency used (400 mg every eight hours, six total doses) are higher than the current trial.³⁶ Additional safety data have been published in various adult settings. McLellen et al. provide a thorough review of the adult literature relating to caffeine use and side effects.³⁷ The following side effects and risks of acute caffeine intake have been documented:

- Anxiety
- Irritability
- Gastrointestinal distress
- Tremors
- Nervousness
- Sleep disruption

Side effects have generally occurred with relatively high doses (600 mg)^{38,39} and/or in participants with excessive sensitivity (e.g., genetic polymorphisms, non-regular consumers).^{40,41} Case reports have demonstrated associations between caffeine intake and increased seizure frequency, particularly in the setting of (1) relatively high doses and (2) pre-existing history of epilepsy.^{42,43} A subsequent large population-based study did not reveal an adjusted association with habitual caffeine intake and seizure history.⁴⁴ Whether caffeine acts as a common seizure trigger is unclear,⁴⁵ but additional precipitating factors (e.g., sleep disturbances) are common in the perioperative setting⁴⁶ which may exacerbate epileptiform activity and seizure risk.

The effects of acute caffeine intake on cardiac arrhythmia risk have also been studied for several years across diverse patient populations. The table below summarizes studies examining acute caffeine administration in relation to cardiovascular physiologic perturbations.

Year	Authors	Sample size (n)	Description

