In the chronic setting, caffeine has also been studied in relation to cardiovascular health and outcomes. Major, representative studies are outlined below:

Year	Authors	Sample size (n)	Description
1999	de Vreede-Swagemakers JJ et al. ⁵⁷	117	>10 cups of coffee per day was associated with sudden cardiac arrest in patients with coronary artery disease
2005	Frost L and Vestergaard p ⁵⁸	47,949	No association between caffeine consumption and risk of atrial fibrillation or flutter
2006	Lopez-Garcia E et al. ⁵⁹	128,493	No association between coffee consumption and coronary heart disease
2010	Reis JP et al. ⁶⁰	5,115	No substantial association between coffee or caffeine intake and coronary and carotid atherosclerosis

The Caffeine, Postoperative Delirium, And CHange IN Outcomes after Surgery-2 (CAPACHINOS-2) Study Protocol <2.0>

Version <2.0>
<14 December 2022>

2011	Klatsky AL et al. ⁶¹	130,054	An inverse relationship was demonstrated between habitual caffeine intake and hospitalization for arrhythmias
------	---------------------------------	---------	---

Chronic caffeine consumption does not appear to be associated with adverse cardiovascular outcomes in the non-surgical setting.

Overall, the weight of available evidence suggests that caffeine administration is not associated with major adverse cardiovascular perturbations (in both acute and chronic settings), particularly at moderate doses consistent with those chosen for this trial. In the perioperative setting, caffeine may reduce risk of rebound headache in habitual users, though caffeine has also been associated with increased postoperative nausea and vomiting. Additional side effects, such as tremors, nervousness, gastrointestinal distress, anxiety, irritability, and sleep disruption remain possible.

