4.3 JUSTIFICATION FOR DOSE

The study drug, either caffeine citrate or D5W (placebo), will be administered as an intravenous infusion starting at the beginning of surgical closure and again on the first two postoperative mornings. The infusion will be given over a 30-minute timespan. The two caffeine arms, 1.5 mg/kg and 3 mg/kg were carefully chosen based on preliminary data and literature review. Dosing will be based on total body weight.⁷²

The lower dose of 1.5 mg/kg may be appropriate for such an older population. First, the reduced dose might lower the risk of adverse side effects (e.g., nausea, vomiting, anxiety).³⁶ Second, our preliminary trial was based on a younger population (mean [\pm standard deviation] age [years]: 52 \pm 17), and the cognitive effects of caffeine may be more pronounced in older populations.⁷³ Lastly, serum caffeine concentration increases with age, as the total volume of caffeine distribution is reduced in older patients.⁷⁴ As such, higher peak serum caffeine concentrations are observed with advancing age after both intravenous and oral administration.⁷⁴

The higher dose of 3 mg/kg might provide added cognitive benefit.³⁷ In fact, the mean, weight-based dose for participants receiving caffeine *and not experiencing any delirium* in our preliminary trial was 3 mg/kg.²⁰ Additive cognitive benefit has also been observed with this dose, particularly for domains relevant to delirium (e.g., attention, vigilance)⁷⁵⁻⁷⁸ and after sleep deprivation,⁷⁹ which is commonly experienced in the hospital setting. Nonetheless, this higher dose may also be associated with additional side effects (e.g., anxiety, GI distress, nausea/vomiting), so multiple dosing arms will help to determine optimal perioperative doses that maximize benefit-to-risk ratios across each postoperative day.

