5.2 EXCLUSION CRITERIA

An individual who meets any of the following criteria will be excluded from participation in this study:

1. Emergency surgery
2. Outpatient surgery
3. Severe cognitive impairment precluding the capacity for informed consent
4. Seizure disorder history
5. Intolerance or allergy to caffeine (based on subjective reporting or objective documentation)
6. Weight >130 kg (as a 3 mg/kg dose would approach the upper limit of daily intake recommended by the FDA)
7. Enrollment in conflicting research study
8. Patients in acute liver failure
9. Acute kidney injury preoperatively
10. Diagnosis of pheochromocytoma
11. Severe audiovisual impairment
12. Non-English speaking

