8.3.4 TIME PERIOD AND FREQUENCY FOR EVENT ASSESSMENT AND FOLLOW-UP

The occurrence of an adverse event (AE) or serious adverse event (SAE) may come to the attention of study personnel during study visits and interviews of a study participant presenting for medical care, or upon review by a study monitor.

All AEs including local and systemic reactions not meeting the criteria for SAEs will be captured on the appropriate case report form (CRF). Information to be collected includes event description, time of onset, clinician's assessment of severity, relationship to study product (assessed only by those with the training and authority to make a diagnosis), and time of resolution/stabilization of the event. All AEs occurring while on study must be documented appropriately regardless of relationship. All AEs will be followed to adequate resolution.

Any medical condition that is present at the time that the participant is screened will be considered as baseline and not reported as an AE. However, if the study participant's condition deteriorates at any time during the study, it will be recorded as an AE.

Changes in the severity of an AE will be documented to allow an assessment of the duration of the event at each level of severity to be performed. AEs characterized as intermittent require documentation of onset and duration of each episode.

The study team will record all reportable events with start dates occurring any time after informed consent is obtained until 7 (for non-serious AEs) or 30 days (for SAEs) after the last day of study participation. At each study visit, the investigator will inquire about the occurrence of AE/SAEs since the last visit. Events will be followed for outcome information until resolution or stabilization.

All serious, unexpected, and probably related events must be reported to the study principal investigator, [name] ([contact]).

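### The caffeine adverse events listed for reporting in Protocol 9.4.4 do not match the risks named in 2.3.1 and 4.3; anxiety is the clearest gap

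*Protocol*

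**What the plan says.** Section 9.4.4 of the protocol says that some risks have been linked to caffeine, refers the reader to Section 2.3, and introduces its table with "The following adverse events that may occur with caffeine will be reported". The table has nine rows: new cardiac arrhythmia, systolic pressure, diastolic pressure, heart rate, restraint use, injury to self or others, the Postoperative Nausea and Vomiting Intensity Scale score, dehydration and allergic reaction. Events outside the table are to be coded under Section 8.3.

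Section 2.3.1 opens its own list with "The following side effects and risks of acute caffeine intake have been documented" and gives six bullets: anxiety, irritability, gastrointestinal distress, tremors, nervousness and sleep disruption. Its closing summary repeats all six: "Additional side effects, such as tremors, nervousness, gastrointestinal distress, anxiety, irritability, and sleep disruption remain possible".

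Section 4.3 ties harm to dose. It suggests that the lower dose might reduce side effects, with anxiety among the examples, and says that "this higher dose may also be associated with additional side effects (e.g., anxiety, GI distress, nausea/vomiting), so multiple dosing arms will help" to find the dose with the best balance of benefit and risk. Section 4.2 gives the same reason for having more than one caffeine arm.

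On data capture, Section 8.3.4 says "At each study visit, the investigator will inquire about the occurrence of AE/SAEs since the last visit", and requires every adverse event on study to be documented whatever its relationship to the drug.

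**The concern.** A safety section that cites a risk section as its source should report the risks named there. Here the two lists differ. Most of the named neuropsychiatric and somatic side effects of caffeine are missing from the table, while dehydration, restraint use and injury, which the text of Section 2.3 does not mention, are in it.

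The dose question is what is at stake. The risk half of that question needs the events that the protocol expects to rise with dose. If the results follow the 9.4.4 list as written, they could show nausea and vomiting by arm but not anxiety, although 4.3 names both. If the categories are chosen only after the data are seen, the choice of which symptoms to show is open to criticism.

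**Working it through.** No figure in the plan bears on this point, so the check sets the lists side by side.

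**Step 1: the six bullets in 2.3.1 against the nine rows in 9.4.4.**

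| Side effect in 2.3.1 | Row in 9.4.4 |
|---|---|
| Anxiety | none |
| Irritability | none |
| Gastrointestinal distress | in part (nausea and vomiting score) |
| Tremors | none |
| Nervousness | none |
| Sleep disruption | none |

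Result: 5 of 6 have no row and 1 of 6 is partly covered.

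**Step 2: all risks discussed in 2.3.1.** Add nausea/vomiting, arrhythmia, raised blood pressure and seizure to the six bullets: 6 + 4 = 10. Nausea/vomiting, arrhythmia and blood pressure have rows (3). Gastrointestinal distress is partly covered (1). The remaining 10 − 3 − 1 = 6 have none: the five above and seizure. Seizure stands apart, for the reasons given under the objection.

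**Step 3: the three examples of dose-related cost in 4.3.** Nausea/vomiting has a row, gastrointestinal distress is partly covered and anxiety has none. Anxiety is named on both sides of the argument in 4.3, as something that the lower dose might reduce and the higher dose might increase.

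**Step 4: does another part of the protocol supply the missing reporting?**
- Section 8.3 covers definitions, severity, causality, capture and reporting to oversight bodies. It states no summary of these events by arm.
- Section 8.2 lists the safety assessments and does not name these symptoms.
- Agitation on the Richmond scale (+2 to +4) is a secondary endpoint in Section 3. It is at most a partial proxy for irritability or nervousness and does not address tremor or sleep.

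So the events are collected, but the protocol names no reported outcome for them.

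**The case against.** The best case on the other side has four parts.

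*The table is not closed.* Section 9.4.4 sends all other adverse events to Section 8.3, which has them recorded with onset, severity, relationship and resolution. This stands: no data are lost. A reader might infer that these harms will be left out of the results, or that the higher dose will therefore look safer than it is. The documents support neither. Nothing says that coded events will be withheld, and the direction of any difference between arms is unknown.

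*Tabulation by arm is commonly left to the analysis plan.* This also stands, and missing table detail would be no finding. But the protocol does more than stay silent. It states which caffeine events will be reported and names the section they come from, and the two disagree.

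*The longest-discussed risks are covered, and the other rows have a purpose.* Cardiovascular effects and nausea/vomiting all have rows. Section 8.2 links restraint use and injury to altered mental status, which suits a delirium trial. Section 2.3.1 also cites a package insert that may be the source of other rows. No row needs to be removed.

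*Seizure is handled elsewhere.* A reader might count it among the omitted caffeine harms. Section 2.3.1 does note that "Case reports have demonstrated associations between caffeine intake and increased seizure frequency", but it also cites a large population study with no adjusted association and concludes that "Whether caffeine acts as a common seizure trigger is unclear". Section 5.2 excludes "Seizure disorder history", and Section 7.1 names seizure as a reason for stopping the drug, with that reason recorded. It is therefore not part of this point.

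A reader might also see a conflict with 8.3.8, which declares events of special interest not applicable. Reconciling 9.4.4 with 2.3.1 and 4.3 does not require changing that section.

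**Conclusion.** The point holds as a mismatch between stated lists. Five of the six side effects bulleted in 2.3.1 have no row in 9.4.4, and gastrointestinal distress is covered only in part. Anxiety matters most, because 4.3 makes it part of the dose comparison. The consequence is a possible omission from the reported outcomes, not a failure to collect data. The primary endpoint and its analysis are unaffected.

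This rests on two readings: that the table is meant to represent the Section 2.3 risks, as its introduction implies, and that coding under 8.3 does not by itself commit the trial to a comparison by arm. No power statement belongs here, since the protocol gives no expected rates for these symptoms.

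**What to change.** Reconcile 9.4.4 with 2.3.1 and 4.3 by adding four incidence rows, taken from the adverse event forms already completed at each visit:
- anxiety, nervousness or irritability;
- tremor;
- sleep disruption;
- gastrointestinal distress other than nausea and vomiting.

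Report each by arm, with risk differences versus placebo and between the two doses and 95% confidence intervals. Fix the grouping of terms before unblinding, so that the choice of harms to show cannot depend on the results. The existing rows stay.

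The cost is wording and four table rows, with no new assessment, visit or staff. The limitation is that mild symptoms elicited by a general question are likely to be under-reported in all arms, perhaps more so in sedated or delirious patients. Blinding limits bias from knowledge of allocation but does not restore the missed events, so the rows should be labelled descriptive.

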9.4.5 BASELINE DESCRIPTIVE STATISTICS

Study arms will be compared on baseline characteristics, including demographics and medical comorbidities. Absolute standardized differences will be used to compare groups at baseline.

9.4.6 PLANNED INTERIM ANALYSES

No formal interim analyses are planned with respect to intervention efficacy. However, interim safety reviews may be conducted at the discretion of the Data and Safety Monitoring Board (DSMB). Any serious adverse event occurring during the study infusion, that may be related to drug administration, will trigger a stopping of drug administration. Drug infusion may also be stopped at the discretion of the clinical or research team for any additional concern not previously described.

9.4.7 SUB-GROUP ANALYSES

A trial subgroup analysis will be conducted in patients meeting criteria for Mild Cognitive Impairment at preoperative baseline (anticipated n=50)⁹¹ based on preoperative AD8 screening, Montreal Cognitive Assessment score <26, and preserved functional independence via cognitive Independent Activities in Daily Living. This subgroup analysis will test the hypothesis that preoperative Mild Cognitive Impairment will be associated with deviations in baseline neural criticality, based on surrogate electroencephalographic (EEG) measures.^{21,92} As a secondary analysis, we will determine whether caffeine exerts a differential effect on cognitive outcomes in patients with Mild Cognitive Impairment, based on our evidence that caffeine may improve neural criticality, and criticality breakdowns are postulated to underlie Mild Cognitive Impairment and Alzheimer's disease.^{21,92,93} Delirium incidence, severity, and Montreal Cognitive Assessment scores one month post-discharge will also be compared in those with and without baseline Mild Cognitive Impairment.

9.4.8 TABULATION OF INDIVIDUAL PARTICIPANT DATA

Individual data will not be tabulated for this study.

9.4.9 EXPLORATORY ANALYSES

The Caffeine, Postoperative Delirium, And CHange IN Outcomes after Surgery-2 (CAPACHINOS-2) Study Protocol <2.0>

Version <2.0>
<14 December 2022>

As a secondary trial analysis, an additional aim will be to identify the underlying cortical dynamics of postoperative delirium. We will perform advanced EEG analysis with a high-density, whole-scalp system, on all clinical trial patients at preoperative baseline and during postanesthesia care unit (PACU) recovery. A separate, low-density EEG system will be used during each of the first two postoperative mornings. Based on our preliminary data,^{21,92} we hypothesize that Deviations from neural criticality, based on EEG-based surrogate markers, will occur during delirium. The impact of caffeine on neural criticality will also be tested, and network-based measures (e.g., global efficiency, hub structure, connection strength, etc.) will also be analyzed.

10 SUPPORTING DOCUMENTATION AND OPERATIONAL CONSIDERATIONS

10.1 REGULATORY, ETHICAL, AND STUDY OVERSIGHT CONSIDERATIONS

10.1.1 INFORMED CONSENT PROCESS

10.1.1.1 CONSENT/ASSENT AND OTHER INFORMATIONAL DOCUMENTS PROVIDED TO PARTICIPANTS

Consent forms describing in detail the study intervention, study procedures, and risks are given to the participant and written documentation of informed consent is required prior to starting intervention/administering study intervention. Written consent materials are submitted with this protocol.

10.1.1.2 CONSENT PROCEDURES AND DOCUMENTATION

Informed consent is a process that is initiated prior to the individual's agreeing to participate in the study and continues throughout the individual's study participation. Consent forms will be Institutional Review Board (IRB)-approved and the participant will be asked to read and review the document. The investigator will explain the research study to the participant and answer any questions that may arise. A verbal explanation will be provided in terms suited to the participant's comprehension of the purposes, procedures, and potential risks of the study and of their rights as research participants. Participants will have the opportunity to carefully review the written consent form and ask questions prior to signing. The participants should have the opportunity to discuss the study with their family or surrogates or think about it prior to agreeing to participate. The participant will sign the informed consent document prior to any procedures being done specifically for the study. Participants must be informed that participation is voluntary and that they may withdraw from the study at any time, without prejudice. A copy of the informed consent document will be given to the participants for their records. The informed consent process will be conducted and documented in the source document (including the date), and the form signed, before the participant undergoes any study-specific procedures. The rights and welfare of the participants will be protected by emphasizing to them that the quality of their medical care will not be adversely affected if they decline to participate in this study.

10.1.2 STUDY DISCONTINUATION AND CLOSURE

This study may be temporarily suspended or prematurely terminated if there is sufficient reasonable cause. Written notification, documenting the reason for study suspension or termination, will be provided by the suspending or terminating party to the investigator, funding agency, the Food and Drug Administration, and other regulatory authorities as needed. If the study is prematurely terminated or suspended, the Principal Investigator (PI) will promptly inform study participants, the Institutional Review Board (IRB), and sponsor and will provide the reason(s) for the termination or suspension. Study participants will be contacted, as applicable, and be informed of changes to study visit schedule.

The CAffeine, Postoperative Delirium, And CHange IN Outcomes after Surgery-2 (CAPACHINOS-2) Study Protocol <2.0>

Version <2.0>
<14 December 2022>

Circumstances that may warrant termination or suspension include, but are not limited to:

- Determination of unexpected, significant, or unacceptable risk to participants
- Insufficient compliance to protocol requirements
- Data that are not sufficiently complete and/or evaluable
- PI decision
- Sponsor decision
- Regulatory and/or other oversight body decision

Study may resume once concerns about safety, protocol compliance, and data quality are addressed, and satisfy the sponsor, IRB and/or FDA.

